6.1.3 Treatments and Dosing

Eligible subjects in the DB phase will be randomized into 1 of 4 double-blind treatment arms using an interactive (voice/web) response system (IVRS/IWRS). The 4 treatment groups include (1) high-dose AZM (AZM-H), (2) intermediate-dose AZM (AZM-M), or (3) low-dose AZM (AZM-L) or (4) losartan.

The dose taken by each subject will be dependent on treatment assignment. All subjects randomized to AZM will initiate treatment at 10 mg. Subjects assigned to AZM-M will be force-titrated at Week 2 to the final randomized dose of 20 mg which will be maintained for the final 4 weeks of the DB Phase. Subjects assigned to the AZM-H group will be force-titrated at Week 2 to the final randomized dose of 40 mg or 80 mg, with the lower of the 2 possible doses being received by subjects who weigh <50 kg and the higher dose being received by subjects who are ≥ 50 kg. Similarly, subjects who are randomized to losartan will initiate treatment at a low dose (25/50 mg) and force titrated at Week 2 to the final losartan dose (50/100 mg). The low dose and final dose of losartan given is based on the subject's weight strata (25 to < 50 kg; ≥ 50 kg). Please see [Section 8.1.3](#) for more information on study medication.

In the Withdrawal Phase, subjects will be re-randomized using IVRS/IWRS to continue receiving their previously assigned active treatment or placebo.

At the beginning of the OL Phase, all subjects will be dispensed AZM 10 mg, which can be titrated to higher dose(s) (up to 40 mg for subjects <50 kg or up to 80 mg for subjects ≥ 50 kg) and additional medication(s) may be added if needed to achieve BP targets during the OL extension. Because body weight is likely to change, dose adjustments may occur during the OL Phase if growth assessments (height and weight) made at Week 8/Visit 9 or at any visit scheduled during the extension necessitate a dose by weight adjustment.

6.1.4 Double-Blind, Randomized Treatment Phases

6.1.4.1 Double-Blind Phase

Qualified subjects who meet the BP entry requirements (ie, seDBP ≥ 95 th percentile for age, gender, and height or ≥ 90 th percentile for age, gender, height if chronic renal disease, diabetes, heart failure or hypertensive target organ damage is present), including at Day -1/Visit 3 (or Day 1 for subjects not participating in ABPM) will be eligible for randomization. Currently treated subjects who have washed out of their antihypertensive medications but have a BP that remains

below the entry criteria at Day -1 (or Day 1 for subjects not participating in ABPM) may extend the Washout/Run-in Period as described in [Section 6.1.2](#) as long as SBP also remains below the same threshold.

After a qualifying clinic seDBP has been confirmed and anthropomorphic measurements have been recorded, subjects who agree to participate in the ABPM procedure will be fitted with an ABPM device that will be worn for at least 24 hours. After the ABPM device is removed on Day 1/Visit 4, pretreatment vital signs and a full panel of clinical laboratory tests will be completed. Subjects who do not participate in the ABPM procedure will not visit the clinic on Day -1; for these subjects, the qualifying seDBP will be confirmed on Day 1 before randomization.

After the baseline procedures are conducted on Day1/Visit 4, all qualifying subjects will receive their first dose of randomized, double-blind study medication at the investigative site, and study medication will be dispensed. Study medication will be administered orally with water, at an agreed upon (by the site and subject) consistent time of day, with or without food, and will be administered in the clinic on days when a visit is scheduled.

Additional clinic visits will be scheduled at Weeks 2, 4, and 6 of the DB Phase. A renal subpanel (sodium, potassium, chloride, blood urea nitrogen [BUN], creatinine, cystatin C, estimated glomerular filtration rate [eGFR]) will be collected at Week 4/Visit 6, which corresponds to 2 weeks after study drug is force-titrated. The renal subpanel may be completed at an earlier unscheduled visit (ie, 5 to 7 days after Week 2/Visit 5) at the investigator's discretion.

An ABPM fitting visit will be scheduled the day before Week 6 (ie, Week 6 -1 Day) for subjects who have a baseline ABPM that meets quality criteria at Day1/Visit 4. Each subject will have the ABPM device removed the following day at Week 6/Visit 8, at least 24 hours after the fitting. During the DB Phase, blood sampling will be performed for population pharmacokinetics. Please see [Table 9.b](#) for a full list of the procedures to be completed during the DB Phase.

6.1.4.2 Withdrawal Phase

The first dose of study drug of the Withdrawal Phase will be administered at Week 6/Visit 8 after removal of the ABPM device (if applicable) and the final trough vital sign measures of the DB Phase are recorded. Study drug will also be dispensed at Week 6. Subjects will return to the clinic at Week 8/Visit 9 for a vital sign assessment, a full panel of clinical laboratory tests, a physical examination, ECG, and to begin the OL Phase.

Please see [Table 9.b](#) for a full list of the procedures to be completed during the Withdrawal Phase.

6.1.5 Open-Label Phase

Subjects will receive their first dose of OL AZM in the clinic and study drug will be dispensed at Week 8/Visit 9 after the final trough vital sign measures of the Withdrawal Phase are recorded. Each subject will also be provided with a home blood pressure monitoring (HBPM) device and a BP diary so that daily BP measures can be recorded and reviewed by the investigator during the OL Phase (see [Section 9.1.16](#)).

Instructions for drug administration during the OL Phase will be the same as during the double-blind (DB) phases; ie, study medication will be administered orally with water, at an agreed upon (by the site and subject) consistent time of day, with or without food, and will be administered in the clinic on days when a visit is scheduled.

[figure not shown]
Throughout the OL Phase, subjects will be treated to achieve and maintain a target BP of <90th percentile for age, gender, and height. For subjects with CKD, a lower BP target may be utilized at the investigator's discretion. Evidence suggesting lower BP targets are appropriate and improve renal outcomes in this patient population is summarized in [Section 6.2.6](#).

All subjects will start the OL Phase receiving AZM 10 mg which can be titrated to higher dose(s) (up to 40 mg for subjects <50 kg or up to 80 mg for subjects \geq 50 kg), and additional antihypertensive medications can be added if needed to achieve target BP. If add-on therapy is needed, the type of medication added (eg a calcium channel blocker, such as amlodipine, a diuretic, such as hydrochlorothiazide, or a beta-blocker such as metoprolol) will be determined per the investigator's clinical judgment. The recommended treatment algorithm for the OL Phase is provided in [Figure 6.b](#).

In the event that down-titration or temporary or permanent discontinuation of antihypertensive medication is indicated, dose reduction or discontinuation should begin with the additional antihypertensive drug(s) first, before the dose of AZM is reduced or discontinued. During the OL Phase subjects may continue participation in the study if AZM is temporarily discontinued for less than 2 weeks. Treatment with a dose of AZM that is above the highest dose allowed for the body weight category (ie, to 80 mg in a subject <50 kg) is not allowed.

Because body weight is likely to change during the study, dose adjustments may occur in the OL Phase if growth assessments (height and weight) made at Week 8/Visit 9 or at any visit scheduled during the extension necessitate a dose by weight adjustment.

Figure 6.b Titration Algorithm for the Open-Label Extension Phase

anti-HTN=antihypertensive

Note: Maximum dose of AZM is dependent upon weight. Subjects ≥ 50 to < 50 kg can be titrated to 20 or 40 mg. Subjects ≥ 50 kg can be titrated to 20, 40 or 80 mg.

(a) Adjustments to medications can occur at unscheduled visits as well as at the scheduled visits shown. However, it is recommended that subjects are treated for approximately 4 weeks at the same dose level before any dose change and/or additional medication is introduced unless there are reasonable medical and/or safety concerns. Investigators will be required to discuss such cases with the medical monitor and provide the rationale for changes outside of the algorithm.

(b) For subjects whose BP is controlled and medications remain unchanged, subsequent visits will be scheduled at 8-week intervals. If further medication adjustment is needed, the subject will be required to return to the clinic within 2 to 4 weeks after each change until medications are stable.

(c) The type of antihypertensive medication (eg a calcium channel blocker, such as amlodipine, a diuretic, such as hydrochlorothiazide, or a beta-blocker such as metoprolol) added will be determined per the investigator's clinical judgment.

The first scheduled titration visit of the OL Phase is at Week 12/Visit 10, which is 4 weeks after initiation of OL treatment; however, an additional unscheduled visit may be requested earlier at the investigator's discretion to titrate subjects not controlled on the initial AZM 10 mg dose. After

CONFIDENTIAL

Week 12, for subjects whose BP is controlled and medications remain unchanged, visits will be scheduled at 8-week intervals (ie, Weeks 20, 28, 36, 44, and 52). However, if further medication adjustment is needed, the subject will be required to return to the site for a vital sign evaluation at an unscheduled visit within 2 to 4 weeks after each change until medications are stable.

Investigators may request laboratory tests (including the renal safety laboratory subpanel: sodium, potassium, chloride, BUN, creatinine, cystatin C, eGFR) if deemed clinically necessary during unscheduled visits. While adjustments to antihypertensive medications can occur at scheduled and unscheduled visits, it is recommended that subjects are treated for approximately 4 weeks at the same dose level before any dose change and/or additional medication is introduced unless there are reasonable medical and/or safety concerns. Investigators will be required to discuss such cases with the medical monitor and provide the rationale for changes outside of the algorithm provided in [Figure 6.b](#).

An optional third ABPM may be completed at the day before Week 52/Visit 16 (ie, Week 52 -1 Day) for subjects that had a baseline ABPM that met quality criteria, and subjects who participate in this procedure will return to the clinic at Week 52/Visit 17 approximately 24 hours after it is fitted for removal of the device and visit procedures.

Upon initiation of the OL Phase (Week 8/Visit 9), subjects and their parents/legal guardians, will be provided with an automated HBPM device and instructed to measure the subject's BP at home at least once daily for the remainder of the study, preferably immediately before dosing. A BP diary will be provided so that the daily measurements can be recorded and reviewed by the investigator. At each visit, the investigator will provide the subject (and parent/legal guardian) with a BP threshold and instructions to contact the investigative site if BP is at or above this threshold. The recommended threshold that would prompt contact with the site is an SBP and/or DBP by HBPM that is 15 or 10 mm Hg, respectively, above the 99th percentile for age, gender, and height [\[5\]](#). See [Section 7.5](#) for a description of criteria for withdrawal due to elevated blood pressure.

Each subject will be followed at a clinic visit approximately 2 weeks after study completion (ie, Week 54/Visit 17) or discontinuation for a health status update and AE assessment.

Please see [Section 9.3](#) for a complete list of the procedures to be completed during the OL Phase.

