Additional clinic visits will be scheduled at Weeks 2, 4, and 6 of the DB Phase. During the DB Phase blood sampling will be performed for population pharmacokinetics.

The first dose of study drug of the Withdrawal Phase will be administered at Week 6/Visit 8 after removal of the ABPM device (if applicable) and the final trough vital sign measures of the DB Phase are recorded. Study drug will also be dispensed at Week 6. Subjects will return to the clinic at Week 8/Visit 9 to begin the OL Phase. The first dose of study drug of the OL Phase will be administered at Week 8/Visit 9 after the final trough vital sign measures of the Withdrawal Phase are recorded.

At the beginning of the OL Phase, all subjects will be dispensed AZM 10 mg which can be titrated to higher dose(s) (up to 40 mg for subjects <50 kg or up to 80 mg for subjects \geq 50 kg) and additional antihypertensive medication may be added if needed to achieve and maintain a target BP of <90th percentile for age, gender, and height. For subjects with chronic kidney disease, a lower BP target may be utilized at the investigator's discretion. If add-on therapy is needed, the type of medication (eg a calcium channel blocker, such as amlodipine, a diuretic, such as hydrochlorothiazide, or a beta-blocker such as metoprolol) added will be determined per the investigator's clinical judgment. Because body weight is likely to change, dose adjustments may occur during the OL Phase if growth assessments (height and weight) made at Week 8/Visit 9 or at any visit scheduled during the extension necessitate a dose by weight adjustment.

In the event that down-titration or temporary or permanent discontinuation of antihypertensive medication is indicated, dose reduction or discontinuation should begin preferably with the additional antihypertensive drug(s) first, before the dose of AZM is reduced or discontinued. During the OL Phase subjects may continue participation in the study if AZM is temporarily discontinued for less than 2 weeks. Treatment with a dose of AZM that is above the highest dose allowed for the body weight category (ie, 80 mg in a subject <50 kg) is not allowed.

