The first scheduled titration visit of the OL Phase is at Week 12/Visit 10, which is 4 weeks after the initiation of OL treatment; however, an additional unscheduled visit may be requested earlier at the investigator's discretion to titrate subjects not controlled on the initial AZM 10 mg dose. After Week 12, for subjects whose BP is controlled and medications remain unchanged, visits will be scheduled at 8-week intervals (ie, Weeks 20, 28, 36, 44, and 52). However, if further medication adjustment is needed, the subject will be required to return to the site for a vital sign evaluation at an unscheduled visit within 2 to 4 weeks after each change until medications are stable. Investigators may request laboratory tests (including the renal safety laboratory subpanel: sodium, potassium, chloride, blood urea nitrogen, creatinine, cystatin C, estimated glomerular filtration rate [eGFR]) if deemed clinically necessary during unscheduled visits.

While adjustments to antihypertensive medications can occur at scheduled and unscheduled visits, it is recommended that subjects are treated for approximately 4 weeks at the same dose level before any dose change and/or additional medication is introduced unless there are reasonable medical and/or safety concerns. Investigators will be required to discuss such cases with the medical monitor and provide the rationale for changes outside of the algorithm provided.

Each subject will also be provided with a home BP monitoring device and a BP diary at Week 8/Visit 9 so that daily BP measures can be recorded and reviewed by the investigator during the OL Phase.

Each subject will be followed at a clinic visit approximately 2 weeks after study completion (ie Week 54/Visit 17) or discontinuation for a health status update and adverse event (AE) assessment.

Primary Objectives:

To evaluate the antihypertensive effect of AZM compared with placebo after a randomized, double-blind, withdrawal (Withdrawal Phase).

Secondary Objectives:

To evaluate the antihypertensive effect of AZM compared with losartan during randomized, double-blind treatment (Double-Blind Phase).

To evaluate the safety and tolerability of AZM relative to placebo and losartan during double-blind treatment, and of AZM during a long-term, OL extension (OL Phase).	
Subject Population: Children aged 6 to <18 years with primary or secondary hypertension.	

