The investigator or designee will instruct the subject or parent/legal guardian on the dosing procedures and study medication storage requirements. Subjects should return their unused study medication at each study visit to allow the opportunity for the investigator or designee to evaluate subjects' compliance with the dosing instructions.

For subjects that choose to participate in the ABPM procedure, the final dose of single-blind placebo run-in investigational medication will be administered in the clinic on Day -1 immediately prior to the Baseline ABPM start. For subjects who do not participate in the ABPM procedure, the final dose of single-blind placebo run-in investigational medication will be administered at home on Day -1.

Eligible subjects will be randomized into 1 of 4 double-blind treatment arms using an IVRS/IWRS. The 3 treatment groups include (1) AZM-L, (2) AZM-M, (3) AZM-H or (4) losartan (**Figure 8.a**).

The tablet strengths taken by each subject will be dependent on treatment assignment. All subjects randomized to AZM will initiate treatment at 10 mg. Subjects assigned to the AZM-M group will be force-titrated at Week 2 to the final randomized dose of 20 mg, which will be maintained for the final 4 weeks of the DB Phase. Subjects assigned to the AZM-H group will be force-titrated at Week 2 to the final randomized dose of 40 mg or 80 mg, with the lower of the 2 possible doses being received by subjects who weigh <50 kg and the higher dose being received by subjects who are ≥ 50 kg.

Similarly, subjects who are randomized to losartan and weighing < 50 kg will initiate treatment at the 25 mg dose and force titrated at Week 2 to the 50 mg losartan dose. Subjects who weigh ≥ 50 kg will initiate treatment at 50 mg and forced titrated at Week 2 to the 100 mg losartan dose.

In the Withdrawal Phase, subjects will be re-randomized using IVRS/IWRS to continue receiving their previously assigned active treatment or placebo.

At the beginning of the OL Phase, all subjects will be dispensed AZM 10 mg, which can be titrated or additional medication may be added if needed to achieve BP targets during the OL extension.

Because body weight is likely to change, dose adjustments may occur during the OL Phase if growth assessments (height and weight) made at Week 8/Visit 9 or at any visit scheduled during the extension necessitate a dose by weight adjustment.

Figure 8.a Treatment Arms

Treatment	Body Weight (a)	Double-Blind, Phase		Withdrawal Phase

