		Wks 0-2	Wks 2-6	Wks 6-8
AZM-L	≥25 to <50 kg	10 mg	10 mg	10 mg or placebo
	≥50 kg	10 mg	10 mg	10 mg or placebo
AZM-M	≥25 to <50 kg	10 mg	20 mg	20 mg or placebo
	≥50 kg	10 mg	20 mg	20 mg or placebo
AZM-H	≥25 to <50 kg	10 mg	40 mg	40 mg or placebo
	≥50 kg	10 mg	80 mg	80 mg or placebo
Losartan	≥25 to <50 kg	25 mg	50 mg	50 mg or placebo
	≥50 kg	50 mg	100 mg	100 mg or placebo

Body Weight (a)	Open-Label Phase	
	Wks 8-12	Wks 12-52
≥25 to <50 kg	AZM 10 mg	AZM 10, 20, or 40 mg (b)
≥50 kg	AZM 20 mg	AZM 20, 40, or 80 mg (b)

L=low, M=intermediate, H=high.(a) The body weight category assigned at Baseline for each subject will remain unchanged throughout the DB Phase and Withdrawal Phase. During the OL Phase, weight category will be determined at each scheduled visit and the dose of medication should be adjusted accordingly.

(b) In the OL Phase, AZM can be titrated and/or other antihypertensive medications can be added to achieve and maintain target BP.

Subjects <50 kg will be required to swallow 2 tablets with a maximum diameter of 7.5 mm and thickness of 4.2 mm and 1 capsule with a maximum length of 15.64 mm and thickness of 7.42 mm as their daily dose. Subjects ≥50 kg will be required to swallow 2 tablets with a maximum diameter of 9.5 mm and thickness of 5.3 mm and 1 capsule with a maximum length of 16.19 mm and thickness of 8.30 mm as their daily dose.

Table 8.a describes the dose and tablet count that will be provided to each group.

Table 8.a Sponsor-Supplied Drug

≥25 to <50 kg – Run-in and Double-Blind Phase (2 tablets+ 1 capsule)

Treatment Group	Dose QD	Treatment Description		
		Active wk 0-2	Active wk 2-6	Placebo(a)
NA	Run-in	NA	NA	One placebo for 20 mg AZM tablet, one placebo for 40 mg AZM tablet, one placebo for O/E losartan capsule
B	AZM Low Dose	One 10 mg AZM tablet	One 10 mg AZM tablet	One placebo for 40 mg AZM tablet, one placebo for O/E losartan capsule
C	AZM Med Dose	One 10 mg AZM tablet	One 20 mg AZM tablet	One placebo for 40 mg AZM tablet, one placebo for O/E losartan capsule
D	AZM High Dose	One 10 mg AZM tablet	NA	One placebo for 40 mg AZM tablet, one placebo for O/E losartan capsule
		NA	One 40 mg AZM tablet	One placebo for 20 mg AZM tablet, one placebo for O/E losartan capsule
E	Comparator	One 25 mg O/E losartan capsule	One 50 mg O/E losartan capsule	One placebo for 20 mg AZM tablet, one placebo for 40 mg AZM tablet

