Treatment Group	Dose QD	Treatment Description	
		Active wk 6-8	Placebo(a)
A	AZM Low Dose Placebo	NA	One placebo for 20 mg AZM tablet, one placebo for 80 mg AZM tablet, one placebo for O/E losartan capsule
B	AZM Low Dose	One 10 mg AZM tablet	One placebo for 80 mg AZM tablet, one placebo for O/E losartan capsule
A	AZM Med Dose Placebo	N/A	One placebo for 20 mg AZM tablet, one placebo for 80 mg AZM tablet, one placebo for O/E losartan capsule
C	AZM Med Dose	One 20 mg AZM tablet	One placebo for 80 mg AZM tablet, one placebo for O/E losartan capsule
A	AZM High Dose Placebo	N/A	One placebo for 20 mg AZM tablet, one placebo for 80 mg AZM tablet, one placebo for O/E losartan capsule
D	AZM High Dose	One 80 mg AZM tablet	One placebo for 20 mg AZM tablet, one placebo for O/E losartan capsule
A	Comparator Placebo	N/A	One placebo for 20 mg AZM tablet, one placebo for 80 mg AZM tablet, one placebo for O/E losartan capsule
E	Compartor	One 100 mg O/E losartan capsule	One placebo for 20 mg AZM tablet, one placebo for 80 mg AZM tablet

(a) The placebo for AZM 20 mg is being used to blind both the AZM 10 mg and AZM 20 mg doses as they are the same shape and size.

Table 8.a Sponsor-Supplied Drug (continued)
– 44 week OL Phase (1 tablet)

Treatment Group	Dose	Treatment Description	
		Active	
≥25 to <50 kg	Treat to Target Blood Pressure	One 10 mg AZM tablet	or
		One 20 mg AZM tablet	or
		One 40 mg AZM tablet	
≥50 kg	Treat to Target Blood Pressure	One 10 mg AZM tablet	or
		One 20 mg AZM tablet	or
		One 40 mg AZM tablet	or
		One 80 mg AZM tablet	

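### Protocol Figure 8.a and SAP Table B start children of 50 kg or more on open-label AZM 20 mg, while the protocol text and SAP 3.3 start everyone on 10 mg

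*Protocol*

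**What the plan says.** **10 mg for everyone.** Protocol 6.1.5: "All subjects will start the OL Phase receiving AZM 10 mg which can be titrated to higher dose(s". The synopsis has the same rule: "At the beginning of the OL Phase, all subjects will be dispensed AZM 10 mg which can be titrated". So do 6.1.3 ("At the beginning of the OL Phase, all subjects will be dispensed AZM 10 mg, which can be titrated") and 8.1.3 ("At the beginning of the OL Phase, all subjects will be dispensed AZM 10 mg"), and SAP 3.3 repeats it. Both the synopsis and 6.1.5 allow an early unscheduled visit "to titrate subjects not controlled on the initial AZM 10 mg dose". The open-label part of Table 8.a includes "One 10 mg AZM tablet" among the supplies for subjects of 50 kg or more.

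**20 mg at 50 kg or more.** The open-label block of Figure 8.a (protocol 8.1.3) gives the heavier group AZM 20 mg in Weeks 8-12. For Weeks 12-52 it gives "AZM 20, 40, or 80 mg (b", where the letter is a footnote mark. SAP Table B has the identical row. In both tables 10 mg appears only for children from 25 kg to below 50 kg.

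The maximum open-label doses, 40 mg below 50 kg and 80 mg at or above it, agree throughout.

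**The concern.** This is a drug-dose instruction for children, and for the heavier group the documents give two answers that cannot both be followed.

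- **First dose.** In the double-blind phase every AZM arm starts low (6.1.3: "All subjects randomized to AZM will initiate treatment at 10 mg"), and 20 mg or more is reached only at Week 2. The disputed row would be the only point in the trial where AZM is started or restarted at 20 mg. Many subjects reach Week 8 without recent AZM. The losartan arm has had none in this trial, and half of the AZM subjects have just spent two weeks on placebo.
- **Later doses.** Under footnote (a) of Figure 8.a, weight category is reassessed at each scheduled open-label visit and the dose follows it. A child controlled on 10 mg who grows past 50 kg would have to move to 20 mg under the figure but could stay on 10 mg under Table 8.a. Down-titration to 10 mg in a heavier child raises the same question.
- **Which dose is assigned.** Protocol 8.1.4 defines overdose against the dose the protocol assigns to the individual. A first dose of 20 mg complies with one rule and exceeds the other.

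**Working it through.** The plan gives no figure to reproduce. The check is a comparison of every statement of the open-label starting dose, followed by simple arithmetic for scale.

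**1. Statements on the starting dose at 50 kg or more**

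| Place | Weeks 8-12 |
|---|---|
| Synopsis, start of open-label phase | 10 mg |
| Synopsis, first titration visit | 10 mg (as the initial dose) |
| Protocol 6.1.3 | 10 mg |
| Protocol 6.1.5, start | 10 mg |
| Protocol 6.1.5, first titration visit | 10 mg (as the initial dose) |
| Protocol 8.1.3, text | 10 mg |
| SAP 3.3, text | 10 mg |
| Protocol Figure 8.a | 20 mg |
| SAP Table B | 20 mg |

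Seven statements give 10 mg and two tables give 20 mg. Two further items bear on the question without naming a start: Table 8.a supplies a 10 mg tablet to this group, and the note under Figure 6.b treats 20 mg as a titration step for it. The Figure 6.b drawing is not in the text available, so any starting dose it shows is unknown.

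**2. Can the two rules be reconciled?**

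- *Superseded text.* No. Neither rule comes from an amendment log.
- *A misread table.* Unlikely. Two documents carry the same row, and the row is coherent in itself: a 20 mg start followed by a range that begins at 20 mg.
- *Dose adjustment for growth at Week 8.* This sentence allows adjustment when a weight change requires it. It does not alter the statement that all subjects are dispensed 10 mg at the start.
- *Footnote (b) of Figure 8.a.* It concerns titration and add-on drugs to reach target blood pressure, not the starting dose.

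The conflict also sits within single sections. Protocol 8.1.3 contains both the 10 mg sentence and Figure 8.a, and SAP 3.3 states 10 mg and then refers the reader to Table B.

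**3. Scale**

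Inputs: at least 213 subjects (protocol 6.1); an approximate 80% cap on subjects of 50 kg or more (6.2.2); 10% dropout (13.3); 1:1:1:1 randomization, then 1:1 withdrawal within each arm (6.1). The weight share and dropout are assumed equal across arms.

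- Illustration: 213 x 0.80 x (1 - 0.10) = 153.4, about 153.
- Lower: 213 x 0.60 x 0.90 = 115.0, using the pre-amendment 60% cap (6.1.1).
- Upper at N = 213: 213 x 0.80 x 1.00 = 170.4, about 170. It rises if N exceeds 213.
- Share with no AZM in Weeks 6-8: losartan arm 1/4, plus AZM subjects switched to placebo 3/4 x 1/2 = 3/8, giving 5/8.
- Of the illustrative 153.4: 153.4 x 5/8 = 95.9, about 96. From the losartan arm, 153.4 x 1/4 = 38.3, about 38.

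**4. Outputs touched**

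Open-label blood pressure is summarized descriptively only (SAP 15.3.3.2). Open-label efficacy and safety are shown overall and by add-on antihypertensive use, not by AZM dose (protocol 13.1.1). The Week 12 blood pressure change is the output most directly exposed. Later visits are touched if the 20 mg floor in the Weeks 12-52 column is applied. The primary and secondary efficacy endpoints are measured at or before Week 8, ahead of the first open-label dose.

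**The case against.** The evidence is lopsided. With seven statements of 10 mg, the Table 8.a supply and the Figure 6.b note on one side, the tables look like a single row error. SAP Table B is a copy of Figure 8.a and adds no independent support for 20 mg. In practice open-label supply is assigned through the IVRS/IWRS (protocol 8.2), which may already enforce one dose. Both doses are given double-blind to subjects of 50 kg or more, and protocol 6.2.2 says 20 mg gives children of 50 to 100 kg exposure similar to that in adults. Only descriptive outputs are involved.

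Most of this is fair, and it limits the size of the point. It does not remove it. The balance of the text suggests 10 mg was meant, but no sentence says the text prevails over the figure, and the IVRS/IWRS setting is not stated. The exposure statement in 6.2.2 could equally be read as a reason for a 20 mg start in heavier children.

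The head-counts are also open to challenge. They use Baseline weight, although weight category is reassessed in the open-label phase. The 60% share is a superseded cap, and 6.1.1 says too few lighter subjects were recruited, so the lower figure is probably too low. They ignore subjects stopped by the Week 8 drug screen. They show scale and are not estimates. Finally, losartan subjects would be taking AZM for the first time in this trial, not necessarily ever, because exclusion 7 admits participants from a single-dose AZM study.

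**Conclusion.** The inconsistency is real and should be fixed. For subjects of 50 kg or more, the first open-label dose is 10 mg by the text and 20 mg by Figure 8.a and SAP Table B. That is a two-fold difference lasting four weeks unless an earlier unscheduled titration occurs. The tables also leave out 10 mg as a later option that Table 8.a allows.

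The group concerned could be most of the trial: about 153 subjects in the illustration and about 115 to 170 across the scenarios at N = 213, under the assumptions stated above.

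Type I error, power and the efficacy conclusions are untouched. The documents do not show that a dosing error occurred or that either starting dose is unsafe. The balance of the text favours 10 mg, but the sponsor has to confirm it.

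**What to change.** Change the open-label row for subjects of 50 kg or more in Figure 8.a and SAP Table B to AZM 10 mg in Weeks 8-12 and AZM 10, 20, 40 or 80 mg in Weeks 12-52. This brings both tables into line with the text and with Table 8.a.

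If the sponsor intended 20 mg, correct the synopsis, 6.1.3, 6.1.5 (including the Figure 6.b note), 8.1.3, Table 8.a and SAP 3.3 instead.

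Either way, confirm that the IVRS/IWRS dispenses the chosen dose.

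The 10 mg correction costs one row in each of two tables, issued as a protocol clarification or amendment with a matching SAP edit, plus the system check. The 20 mg alternative touches more sections. Neither changes the design, sample size or efficacy analyses.
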